## STATISTICAL ANALYSIS

All analysis will be done using SPSS version 22 (SPSS Inc., Chicago, IL, version 16.0 for Windows). Descriptive statistics will be obtained for demographic patient related and treatment related variables. The variance between both the treatment groups will be analysed using two way ANOVA. The primary end points will be compared between the two groups using chi square statistics. As a secondary outcome measure, univariate and multivariate analysis will be done to identify the factors that may influence post operative delirium.

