## **MATERIALS AND METHODS**

The proposed study will be a prospective randomized clinical trial. It will be carried out for a period of 15 months from January 2016 to June 2017 in 60 adult patients scheduled for spine surgery at PGIMER, Chandigarh. Ethical clearance will be sought from the human and ethics committee of the institute. Written informed consent will be taken from all the patients. The patients will be randomly divided into two groups of 30 each - Group I (Isoflurane) and Group D (Desflurane) prior to surgery.

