### **Anaesthesia Protocol**

All the preoperative medications will be continued on the day of surgery. Anaesthesia will be induced with propofol 2-2.5 mg/kg and fentanyl 2 ug/kg. Vecuronium 0.1 mg/kg will be used to facilitate endotracheal intubation. All the patients will be monitored with 5 lead electrocardiogram, pulse oximeter, non-invasive blood pressure, temperature, airway gas levels, end-tidal carbon-dioxide concentration and urine output. Maintenance of anaesthesia will be carried out with either isoflurane or desflurane as per the randomization. The depth of anaesthesia will be monitored using entropy (to keep state entropy between 40 and 60). Analgesia will be maintained with fentanyl 0.5-2 ug/kg/hour and Vecuronium 0.06 mg/kg will be used intermittently for neuromuscular blockade to maintain less than two twitch response on neuromuscular transmission (NMT) monitoring. Replacement fluid will consist of normal saline. Intraoperative haemodynamics, oxygen saturation, temperature and blood loss will be recorded and compared among the two groups. The patients will be administered an antiemetic intraoperatively. At the end of the procedure neuromuscular blockade will be antagonized with neostigmine (0.05mg/kg)

and glycopyrrolate (0.01mg/kg). The patients who cannot be extubated at the end of the procedure will followed up in the postoperative period. The patients who cannot be extubated within forty-eight hours following surgery will be excluded from the study.

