### **Study protocol**

The screening for preoperative cognitive dysfunction will be done using the mini-cog test which includes a three word recall test and clock drawing test. The patients with preoperative cognitive dysfunction will also be included. The primary outcome variable will be assessment of delirium at day one and day three following surgery. Post operative delirium will be diagnosed using the 3D-CAM(Confusion Assessment Method) which tests for four features with a series of questions. The features include 1) acute onset and fluctuating course,2) inattention,3) disorganized thinking and 4) altered level of consciousness. Diagnosis of delirium is made if features 1 and 2 and either 3 or 4 are present. Similarly the severity of POD will be assessed on day one and day three following surgery. Severity of postoperative delirium will be assessed using the CAM-S long form delirium severity score.It asseses ten features including 1) acute onset and fluctuating course,2)inattention,3)disorganized thinking , 4)altered level of consciousness, 5) disorientation, 6)memory impairment ,7)perceptual disturbances ,8)psychomotor agitation, 9)psychomotor retardation and 10) altered sleep-wake cycle. The scores range from 0 to 19.

The demographic data of the patients,type and site of surgery will be noted. Preoperative hemoglobin, serum electrolytes, blood urea and serum creatinine will be recorded. The average of 3 blood pressure (BP) readings measured preoperatively will be recorded as baseline. Intraoperative hemodynamics will be monitored using non invasive blood pressure monitoring. Systolic BP <30% of baseline will be recorded as hypotension and systolic BP >30% will be

recorded as hypertension. The management of intraoperative hypotension and hypertension will be at the discretion of the attending anaesthesiologist. The intraoperative factors like duration of surgery and anaesthesia, use of intravenous fluids , blood loss, number blood units transfused and opioid use will be studied at the time of surgery. The time to emergence and extubation following the completion of surgery will be noted. Emergence time will be the time from cessation of anesthetic agent to the time the patient responds to verbal commands. Extubation time will be the time interval between cessation of anesthetic agent and extubation of trachea.

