The postoperative factors like postoperative pain, nausea and vomiting, fever, hemoglobin, serum electrolytes, blood urea and serum creatinine will be noted.

Preoperative and postoperative pain will be assessed using the numerical rating score on a scale of one to ten.

The association of various preoperative, intraoperative and postoperative factors with POD will be determined.

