### 3. Postoperative Period

The patients will be followed up on day one and day three following surgery. The patient will be subjected to psychological tests for evaluating delirium. Pain scores will be assessed using the numerical rating score. Postoperative factors like nausea and vomiting, fever, hemoglobin, serum electrolytes, blood urea and serum creatinine will be noted.

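### Two-way ANOVA is named for the non-primary comparisons between arms with no variables, second factor or patient term; it is mis-stated for single values and, if patient is ignored, gives wrong error rates for repeated ones

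*Combined protocol and SAP*

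**What the plan says.** The part of STATISTICAL ANALYSIS that deals with tests makes three assignments.

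- Primary end points: "The primary end points will be compared between the two groups using chi square statistics".
- Factors that may influence delirium: univariate and multivariate analysis.
- Everything else between the arms: "The variance between both the treatment groups will be analysed using two way ANOVA".

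The third sentence gives no dependent variables, no second factor and no term for the patient. The design has one randomised factor with two levels: "The patients will be randomly divided into two groups of 30 each" (MATERIALS AND METHODS).

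The variables that could fall under that sentence are of two kinds.

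- **One value per patient.** Blood loss, durations of surgery and anaesthesia, and emergence and extubation times. For example: "Emergence time will be the time from cessation of anesthetic agent to the time the patient responds to verbal commands" (Study protocol).
- **Several values per patient.** CAM-S: "Similarly the severity of POD will be assessed on day one and day three following surgery" (Study protocol). Pain: "Preoperative and postoperative pain will be assessed using the numerical rating score on a scale of one to ten" (Study protocol), with the postoperative visits fixed by "The patients will be followed up on day one and day three following surgery" (Postoperative Period). Intraoperative measurements: "Intraoperative haemodynamics, oxygen saturation, temperature and blood loss will be recorded and compared among the two groups" (Anaesthesia Protocol), with no number of readings given.

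Two baselines are collected: the average of three preoperative blood pressure readings, and the preoperative pain score.

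**The concern.** A two-way ANOVA needs two factors, and the plan supplies one. For a variable measured once, nothing can fill the second place. For a variable measured repeatedly, time is the natural second factor, but an ordinary two-way ANOVA then counts each reading as if it came from a different patient. Readings from one patient are usually correlated, so the residual term no longer measures the uncertainty of a comparison between patients.

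At stake is the reliability of the secondary comparisons between arms: severity, pain and, if analysed as a series, haemodynamics. Two analysts could follow the sentence in good faith, one with a patient term and one without, and reach different p-values from the same data.

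**Working it through.** **1. The plan's own figure.** No figure is given for the ANOVA. The only computed design figure is 60 patients. It reproduces from 27% against 0%, a 5-point margin, power 85% and alpha 0.05 taken as one-sided (the documents do not state sidedness):

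n per arm = (1.645 + 1.036)² × 0.27 × 0.73 / (0.27 − 0.05)² = 29.28, rounded up to 30, so 60 in total.

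The ANOVA does not enter this calculation, so the sample size does not depend on this point.

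**2. Single-value variables.** With one factor of two levels, ANOVA gives F = t² and the same p-value as the t-test. A numerical check with 30 per arm gave t = −1.1987 and F = 1.4369 = 1.1987², with p = 0.2355 from both. The error rate is therefore unharmed; only the description is wrong.

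**3. Repeated variables, patient ignored.** Inputs:

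- 30 patients per arm (documents).
- m readings per patient: 2 for CAM-S and postoperative pain, and 3 for pain if the preoperative score is also entered as a row (documents). For intraoperative series m is not stated; 6 and 12 are assumed for illustration.
- Within-patient correlation ρ: not in the documents; 0.3, 0.5 and 0.7 are assumed.

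The true variance of the difference between arm means is (1 + (m − 1)ρ) times what the ANOVA assumes. The type I error of the group effect is therefore about

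2 × [1 − Φ(1.96 / √(1 + (m − 1)ρ))].

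For m = 2:

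- ρ = 0.3: 1.96/√1.3 = 1.719, giving 8.6%
- ρ = 0.5: 1.96/√1.5 = 1.600, giving 11.0%
- ρ = 0.7: 1.96/√1.7 = 1.503, giving 13.3%

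A null simulation with 20,000 replicates per setting agrees:

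| Readings per patient | ρ = 0.3 | ρ = 0.5 | ρ = 0.7 |
|---|---|---|---|
| 2 | 8.7% | 11.0% | 13.2% |
| 3 | 12.0% | 16.4% | 20.5% |
| 6 (assumed) | 21.0% | 29.2% | 35.6% |
| 12 (assumed) | 34.4% | 44.1% | 50.6% |

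At ρ = 0 there is no inflation (4.7% to 5.1%).

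**4. The interaction goes the other way.** A within-patient contrast has true variance (1 − ρ) times what the ANOVA assumes. The group-by-time test at m = 2 therefore rejects in about 2 × [1 − Φ(1.96/√(1 − ρ))] of null trials: 1.9%, 0.6% and under 0.1% for ρ = 0.3, 0.5 and 0.7. The simulation gave 2.1%, 0.6% and 0.1%. Real differences in time course would tend to be missed.

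**5. Patient as the unit.** A t-test on patient means, which is the between-patient test of a repeated-measures ANOVA, gave 4.6% to 5.2% in every setting.

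**6. CAM-S.** The score runs from 0 to 19. The protocol cites a delirium incidence of 3.3% to 3.8% after spine surgery. In 60 patients that is 60 × 0.033 = 2.0 to 60 × 0.038 = 2.3 cases. A distribution piled up near 0 is therefore likely, though the documents do not state one.

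**The case against.** The strongest reply is that the sentence is under-specified rather than wrong. A group-by-time repeated-measures ANOVA is sometimes loosely called *two way*; it would suit the repeated continuous variables and inflate nothing. This stands in part. A reader might infer that the plan inflates false positives outright. The documents do not support that, because they never say that patient will be ignored. But they do not say the reverse either, and the repeated-measures reading still leaves the single-value variables with a method that does not fit them.

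Other limits also stand.

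- The largest percentages in the table rest on assumed numbers of readings. The protocol also classifies systolic pressure against baseline as hypotension or hypertension, so some haemodynamic data may be analysed as events rather than as a series.
- A reader might infer that a false arm difference in pressure or pain would feed the search for causes of delirium. The second aim has its own univariate and multivariate analysis, and nothing makes these arm comparisons the route to it.
- CAM-S is not explicitly assigned to ANOVA. It is introduced directly after the primary outcome. If it is not covered by the ANOVA sentence, no suitable test for a 0-to-19 score is stated at all.
- Leaving out the baselines from a randomised comparison costs precision; it is not an error.

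**Conclusion.** The point holds in a limited form. As written, the ANOVA sentence cannot be right for variables with one value per patient, although this does not raise their false-positive rate. For repeated variables, and only if patient is ignored, the group effect is tested at about 9%, 11% and 13% instead of 5% at the two documented postoperative readings. More readings would make this worse, and the interaction test becomes too strict. These sizes rest on assumed correlations of 0.3 to 0.7. The primary chi-square comparison is assigned separately and is untouched. The sentence should be rewritten before analysis because it leaves the choice of model, and with it the error rate, to the analyst.

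**What to change.** Replace the ANOVA sentence with a list of variables by type and a method for each.

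- **Single-value variables:** t-test or Mann-Whitney for continuous ones (blood loss, durations, emergence and extubation times); chi-square or exact test for categorical ones.
- **Repeated haemodynamics and day-1/day-3 pain:** a repeated-measures ANOVA or linear mixed model with arm, time and arm-by-time, and patient as the unit. Adjust for the baseline blood pressure average or the preoperative pain score. State how many intraoperative readings enter the model.
- **CAM-S on days 1 and 3:** a rank test between arms on each day.

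Laboratory values are recorded before and after surgery, so the list should say how they are handled too.

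The change is to wording. It needs no new data and no more patients; the baselines are already collected. The cost is slightly more analysis work. The same section names two versions of its statistics package (22 and 16.0), and the version to be used should be settled at the same time.

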### ***POST OPERATIVE DELIRIUM-***

American Psychiatric Association defines delirium as an acute change in cognition or disturbance of consciousness that cannot be attributed to a pre-existing medical condition, substance intoxication or medication. However various conditions such as age, functional status and substance abuse influence the risk of immediate and post operative delirium. Delirium in the

postoperative period can be divided into emergence delirium and post operative delirium depending on the time of presentation. Emergence delirium or emergence agitation is usually observed immediately after GA and is related to anesthetic drugs. It is common in children with peak age being 2-4 years. It is accompanied by psychomotor agitation which includes a series of unintentional and purposeless motion like pacing around a room, wringing ones hands, pulling off clothing, and self-extubation. It usually occurs within the first 10 minutes of recovery and resolves within minutes to hours without long term neurological effects. It is more commonly associated with less soluble inhalational anaesthetics like sevoflurane and desflurane.

Postoperative Delirium(POD) usually presents 24-72 hours following a lucid interval. It usually resolves within hours to days. Post operative delirium can have lasting effects beyond the perioperative period. POD has also been associated with postoperative depression, posttraumatic stress disorder-like syndrome which may impede recovery. As a result, delirium may have long-term mental health complications.

POD has been previously reported to occur following several kinds of surgery, including general surgery , head and neck cancer surgery, cardiac surgery , vascular surgery , hip fracture and joint replacement surgery.The incidence of post operative delirium(POD) in various studies ranges from 5% to 15%.Within certain high-risk groups such as hip fracture patients, the range is 16–62% with an average of 35%. The incidence of POD in spine surgery in previous studies was found to be between 3.3% to 3.8%.

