### **AIMS OF THE STUDY-**

- 1)To compare the incidence of postoperative delirium with isoflurane and desflurane on adults undergoing spine surgery .
- 2)To determine the perioperative factors which can influence postoperative delirium.

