## **STATISTICAL ANALYSIS-**

Sample size calculation-

Incidence of POCD was 0% and 27% in a previously conducted study with 15 patients in each group with the use of desflurane and isoflurane respectively and the reported p value was 0.028.

We used these results to calculate sample size in our study to prove superiority of desflurane over

isoflurane with a margin of atleast 5 percent using an alpha error of 0.05 and power of 85%.The estimated sample size was 60 with 30 in each arm.

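### Aim 2 plans a multivariable search for delirium risk factors, but 60 patients are expected to yield only about 2 to 9 delirium events, and the plan neither limits the model nor calls it exploratory

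*Combined protocol and SAP*

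**What the plan says.** The second of the two stated aims is: "To determine the perioperative factors which can influence postoperative delirium". The Study protocol section widens the scope: "The association of various preoperative, intraoperative and postoperative factors with POD will be determined". The only analysis text is one sentence under Statistical Analysis: "As a secondary outcome measure, univariate and multivariate analysis will be done to identify the factors that may influence post operative delirium". It gives no regression method, candidate list, selection rule, significance threshold, multiplicity rule or provision for sparse events.

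On size, Materials and Methods says: "The patients will be randomly divided into two groups of 30 each". The sample-size paragraph rests on a cognitive-dysfunction outcome, not on delirium: "Incidence of POCD was 0% and 27% in a previously conducted study with 15 patients in each group". It sizes the two-arm comparison only, and nothing is calculated for Aim 2.

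On expected delirium, the Review of Literature says: "The incidence of POD in spine surgery in previous studies was found to be between 3.3% to 3.8" (per cent), and for surgery more widely: "The incidence of post operative delirium(POD) in various studies ranges from 5% to 15" (per cent). The Introduction adds 16–62% for high-risk groups.

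**The concern.** What a risk-factor analysis of a binary outcome can support depends on the number of events, not the number of patients. On the plan's own rates the events number in single figures, while the plan records roughly 30 variables that could be tried and does not say which will be. As written, the analysis would probably miss real factors and could report chance associations as influences on POD. Any adjusted odds ratios could be extreme, undefined, or dependent on which variables happened to be entered.

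A second problem is timing. Postoperative pain, nausea and vomiting, and fever are noted at the same day 1 and day 3 follow-up at which delirium is assessed. An association seen at one visit does not show which came first.

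**Working it through.** **1. The plan's own figure.** The 60 reproduces as a superiority-by-margin calculation with rates 0.27 and 0, margin 0.05, power 85% and alpha 0.05. One-sided alpha is assumed, because the plan does not state sidedness.

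n per arm = 0.27 × 0.73 × (1.645 + 1.036)² / (0.27 − 0.05)² = 0.1971 × 7.188 / 0.0484 = 29.3, rounded up to 30, so 60 in total.

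This concerns the two-arm comparison and gives no support to Aim 2.

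**2. Expected POD events in 60 patients.**
- Spine rate: 60 × 0.033 = 1.98 and 60 × 0.038 = 2.28.
- General rate: 60 × 0.05 = 3 and 60 × 0.15 = 9.
- Sample-size inputs: 30 × 0.27 + 30 × 0 = 8.1. These are cognitive-dysfunction rates, used here only as the plan's most explicit assumption.

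The chance of no event at all at the spine rate is 0.967^60 = 13% or 0.962^60 = 10%.

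**3. Candidate factors (my count; the plan gives none).** Preoperative 11: age, sex, type of surgery, site, haemoglobin, electrolytes, urea, creatinine, baseline blood pressure, Mini-Cog, pain. Intraoperative 10: two durations, fluids, blood loss, units transfused, opioid use, hypotension, hypertension, emergence time, extubation time. Postoperative 7: pain, nausea and vomiting, fever, haemoglobin, electrolytes, urea, creatinine. With group this makes 29, or 27 to 33 under other ways of counting. Events per candidate are 1.98/29 = 0.07 to 9/29 = 0.31.

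The conclusion does not need that count. A model with only three terms has 1.98/3 = 0.66 events per term at the spine rate and 8.1/3 = 2.7 at the sample-size inputs.

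**4. An arm with no events.** With rate p in both arms, P(at least one arm empty) = 1 − [1 − (1 − p)^30]². This is 60% at 3.3%, 53% at 3.8%, 38% at 5% and 2% at 15%. When exactly one arm is empty, ordinary logistic regression has no finite group coefficient, although the other coefficients stay finite. Under the 0% versus 27% inputs the desflurane arm is empty by assumption.

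**5. Separation from other covariates.** These are simulations with 60 patients, group left out, about one third of covariates binary and binary prevalence 10–50% (all assumed). Two runs gave:
- at 2 events: 38–63% of datasets separate with two covariates and 72–84% with five;
- at 8 events: 16–17% with five and 26–30% with ten.

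The result is sensitive to how many covariates are binary; continuous covariates separate less often.

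**6. Univariate power at two-sided 5%.** The binary factor is split 30:30 with odds ratio 3. At 8.1 events the risks are 0.075 and 0.195, since 30 × (0.075 + 0.195) = 8.1. Binary power is by exact enumeration. The continuous factor has odds ratio 2 per SD, by simulation with a t or rank test.

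| Expected events | Binary, Fisher | Binary, uncorrected chi-square | Continuous |
|---|---|---|---|
| 2.0 | 0.2% | 4% | about 13% |
| 3 | 1% | 9% | about 19% |
| 8.1 | 14% | 29% | about 38% |
| 9 | 17% | 31% | 41–44% |

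The chi-square approximation is itself unreliable at these counts.

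**7. Chance findings.** If 29 null factors were each tested at an uncorrected 0.05 (assumed; no threshold is stated), the expected number of false positives is 29 × 0.05 = 1.45. The chance of at least one is 1 − 0.95^29 = 77% if the tests are independent. With discrete tests and correlated factors, simulation gives 58–73% using Fisher for the binary factors and 66–77% using chi-square.

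**The case against.** **The plan does not describe a 30-variable model.** This is right. A reader might infer one from the list of recorded variables, but the text refers only to various factors and to multivariate analysis. Some recorded items have another stated use: "Intraoperative haemodynamics, oxygen saturation, temperature and blood loss will be recorded and compared among the two groups". The fault is an unspecified multivariable analysis with too few events, and separation figures for very large models would describe something nobody planned.

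**Evenly split binary factors are an unfavourable case.** This also stands. Many recorded factors are continuous, and the table shows clearly better power for them, though still below one half. It would likewise be wrong to infer that nothing can reach significance with fewer than six events. Under Fisher's test that holds for an exactly 50:50 factor. With 12 of 60 patients exposed, two events that both fall among the exposed give p = 0.037.

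**The 16–62% range was set aside.** The Introduction attaches it to high-risk groups that include orthopaedic patients. The same documents give a separate and much lower figure for spine surgery, and entry is limited to ages 18–65 and ASA I–II. Even at 62% there would be 60 × 0.38 = 22.8 non-events, or 22.8/29 = 0.8 per candidate.

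**Postoperative factors belong to the aim.** They do. The literature review also names severe acute pain, postoperative transfusion and low postoperative haematocrit as risk factors, and a day 1 factor can precede delirium first seen on day 3. The documents therefore do not support barring every postoperative factor. What they do not justify is reading a same-visit association as an influence on POD.

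**Delirium severity could be analysed instead.** The CAM-S score (0–19) is collected on both days and is not limited by event count in the same way. But the plan does not run the factor analysis on it, and scores may cluster near zero.

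**It is only secondary.** The plan says so, and that limits the weight of the point.

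**Conclusion.** The concern holds, confined to Aim 2. On the documents' own rates the trial should see about 2 events, or at best about 8 or 9. At the lower end a conventional model often has no finite solution even with two covariates. At the upper end a model with several terms can often be fitted but would be unstable. Univariate tests can be run, with low power and a high chance of at least one spurious result if many are done without correction.

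This rests on the stated incidences applying to these patients, on all 60 being analysed (exclusions after randomisation would lower the event count), and on ordinary logistic regression being the method meant, which the plan does not say. The power and separation figures also depend on the effect sizes and covariate mix assumed above.

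Two further inferences are not supported. The 77% is not the share of reported factors that would be false, which the documents do not allow one to compute. And the primary chi-square comparison of the two arms is not affected by this point.

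**What to change.** In the Statistical Analysis section:

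1. Label Aim 2 exploratory.
2. Report unadjusted associations with exact or other small-sample confidence intervals, and state how many factors were examined.
3. Limit any multivariable POD model to anaesthetic group plus one, at most two, preoperative factors named in advance (age or Mini-Cog, for example), fitted by Firth-penalised or exact logistic regression.
4. State in advance a minimum event count below which only the unadjusted results are reported. Do not take six as a general cut-off, since it applies only to an evenly split factor under Fisher's test.
5. Describe postoperative factors separately. Do not interpret those measured at the same visit as POD as influencing it; day 1 factors may be related descriptively to POD first seen on day 3.

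The cost is a few sentences and no new data. The downside is that fewer factors can be called independent predictors, and a procedure outside the named SPSS package may be needed.
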